If independence from active vitamin D and reduction of oral calcium is not achieved on Day 14 (ie, elimination of active vitamine D and reduction of oral calcium to or below 500 mg/day), the AZP-3601 dose will be increased and patients will be treated at this dose for the remaining duration of the treatment period (up to Day 28). In addition, staggered reductions of doses of oral calcium and active vitamin D supplements will therefore be performed and/or continued during the second 14 days of the Main Treatment Period according to the same principles as the first 14 days of the Main Treatment Period.

Patients achieving independence from active vitamin D and reduction of oral calcium on Day 14 will remain at the same dose level. The last remaining daily dose of oral calcium, if any, may be removed on Day 17 based on the predose albumin-corrected value of serum calcium.

Patients will undergo frequent testing for albumin-corrected serum calcium and phosphate during the initial 14-day treatment period and again following increase of the dose. In addition, there may be additional and unscheduled checks for albumin-corrected serum calcium and phosphate at the discretion of the Investigator.

At any time during the study, hypercalcemia and hypocalcemia will be managed by adjustment in active vitamin D and/or oral calcium supplementation. Adjustments will be based on laboratory values including albumin-corrected serum calcium and serum phosphate as well as on symptoms and will be performed at the Investigator's judgment. As a general guidance, adjustments should be performed when calcium values are outside the target range of 7.8 to 9.0 mg/dL, ie, 1.95 to 2.25 mmol/L.

The following treatments are administered in Part C in an open-label fashion:

- Cohort C1: multiple sc doses of 20 µg AZP-3601 (n=12) qd from Day 1 to Day 28 (dose increase of AZP-3601 to 40 µg was allowed from Day 14 onwards)
- Cohort C2^b: multiple sc doses of a fixed dose of 10^a µg AZP-3601 (n=12) qd from Day 1 to Day 28 (dose of AZP-3601 may be increased at a fixed dose of 20^a µg from Day 14 onwards)

During the extension phase, patients may have their AZP-3601 dose increased in increments of 10^a µg to a maximum dose of 60^a µg (Cohort 1) and of 80^a µg (Cohort 2)

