	for supplemental oral calcium treatment ≥1000 mg per day over and above
	normal dietary calcium intake prior to baseline measurements.
	- Part C (Extension phase): Patients entering the extension phase need to
	have completed the Day 28 visit of the Main treatment period and sign the
	ICF before entering the extension phase.
Sex	: Male or female
Age	: 18 to 75 years, inclusive, at screening

Study Drug

Active medication	
Drug product	: AZP-3601
Activity	: PTH analog
In development for	: HP
Strength	:40 μg of AZP-3601 per vial
Dosage form	: Powder for solution for injection
Route of administration	: sc abdominal injection (with rotation of injection sites every dosing day for Parts B and C)
Manufacturer	: NUVISAN GmbH, Neu-Ulm, Germany

Active medication (additional batch for Part C)

Drug product	: AZP-3601
Activity	:PTH analog
In development for	: HP
Strength	:100 μg of AZP-3601 per vial *
Dosage form	: Powder for solution for injection
Route of administration	: sc abdominal injection (with rotation of injection sites every dosing day)
Manufacturer	: NUVISAN GmbH, Neu-Ulm, Germany

Variables* Safety and Tolerability Variables

: Adverse events, clinical laboratory (clinical chemistry, hematology, coagulation, and urinalysis), vital signs (systolic and diastolic blood pressure, pulse rate, and body temperature), 12-lead electrocardiogram and time-matched with PK sampling (Part C), continuous cardiac monitoring (, body weight, physical examination (full or abbreviated), injection site reaction, and presence of antidrug antibodies (ADA) in plasma (ADA for Part C only)

F	or hypocalcemia and hypercalcemia events, time of onset, amount of upplements administered, and timing will be recorded.
PK Variables : -	Plasma AZP-3601 concentrations Plasma PK parameters estimated using noncompartmental analysis, as appropriate.
	Day 1 of Part C: Cmax, tmax, AUC0-t, AUC0-12, and AUC0-24. Day 28 of Part C (Main treatment period) and Day 84 of Part C (Extension phase): Cmax, Ctrough, Cmin, tmax, kel, t1/2, AUC0-12, AUC0-24, CLss/F, Vz/F, and Rac
PD and Other	
Variables : P -	arts C : Levels of serum total calcium, albumin-corrected serum calcium, and serum
-	phosphate. 24-hour urine calcium, phosphate, renal clearance of calcium and phosphate, fractional excretion (FECa) of calcium and phosphate,
	renal tubular maximum reabsorption of phosphate/glomerular filtration rate (TMP/GFR).
-	Endogenous serum PTH(1-84) levels.
: P	arts C only:

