During the main treatment period, patients in Part C will receive AZP-3601 for 28 days as daily sc abdominal injections (with rotation of injection sites every dosing day). Doses of oral calcium and active vitamin D supplements will be carefully reduced during the initial 14 days of treatment while maintaining albumin-corrected serum calcium in the target range (7.8 to 9.0 mg/dL). Reductions of both oral calcium and active vitamin D supplements will be performed using a staged approach until the active vitamin D dose can be eliminated and the oral calcium dose can be reduced to or below 500 mg/day (please note that throughout this protocol doses of oral calcium refer to doses of elemental calcium). Based on animal data, serum calcium is expected to increase progressively following repeated administration of AZP-3601 and PD steady state is expected to be observed within the first 5 days of dosing. Staggered reductions of doses of oral calcium and active vitamin D supplements will therefore be performed at near-steady state based on the predose albumin-corrected serum calcium value. It is anticipated to perform reduction of supplements on Day 5, 8, and 11. The days of dose reduction of supplements may change based on data from Part B; they may be advanced or delayed based on (but not limited to) when the PD steady state is observed.

If independence from active vitamin D and reduction of oral calcium is not achieved on Day 14 (ie, elimination of active vitamine D and reduction of oral calcium to or below 500 mg/day), the AZP-3601 dose will be increased and patients will be treated at this dose for the remaining duration of the treatment period (up to Day 28). Patients achieving independence from active vitamin D and reduction of oral calcium on Day 14 will remain at the same dose level. The last remaining daily dose of oral calcium, if any, may be removed on Day 17 based on the predose albumin-corrected value of serum calcium.

Patients will undergo frequent testing for albumin-corrected serum calcium and phosphate during the initial 14-day treatment period and again following increase of the dose. In addition, there may be additional and unscheduled checks for albumin-corrected serum calcium and phosphate at the discretion of the Investigator.

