8.1.4 Pooling

For each part, summary statistics will be calculated by treatment (and time point, if applicable).

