8.2.2 Treatment/Subject Grouping

Label	Grouping
Study Drug	AZP-3601 and Placebo
Treatment	Port C (MAD Port in Subjects with HD)
	Part C (MAD Part in Subjects with HP) multiple sc AZP-3601
Dose Level ^a	
	Part C (MAD Part in patients with HP, Main Treatment Period) Cohort 1: 20μg qd from Day 1 to Day 28 (may be increased to 40 μg from Day 14 onwards)
	Cohort 2: 40µg qd from Day 1 to Day 28 (may be increased to 60 µg from Day 14 onwards)
	Part C (MAD in patients with HP, Extension Phase)
	During the extension phase, patients may have their AZP-3601 dose increased in increments of 10^a µg to a maximum dose of 60^a µg (Cohort 1) and of 80^a µg (Cohort 2)

^a The planned dose levels may change following review of the emerging data.

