8.5 TFL Layout

Report layout will be according to the PRA EDS – International Council for Harmonisation (ICH) E3 compliant – CSR Template. The layout of TFLs will be according to the PRA EDS standards.

Format:

- Page size: A4
- Data in listings will be sorted by study part, subject number, (for Part C) and time point.
- Data in tables will be sorted by study part, immediately part (for Part C) and time point.
- Column titles will be in title case letters.
- All tables and listings will be in landscape format.

Study part refers to ______ 'Part C Main', and 'Part C Extension' if applicable: "Treatment" refers to placebo and various dose levels of study drug in the TFL.

Table, listing and figure shells will be provided together with the SAP.

EDSREP 009 T 01 G Page 16 of 53

Version Date: 26-Aug-2022

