AUC ₀₋₁₂		Х	Area under the plasma concentration-time curve from time zero up to 12 hours.	AUC0-12 from WNL AUC0-12 will be presented as "AUC(0-12)" in the TFL.
AUC ₀₋₂₄		Х	Area under the plasma concentration-time curve from time zero up to 24 hours.	AUC0-24 from WNL AUC0-24 will be presented as "AUC(0-24)" in the TFL.
k _{el}		X	Terminal phase rate constant calculated by linear regression of the terminal log-linear portion of the concentration vs. time curve. Linear regression of at least three points and an adjusted r² greater than 0.80 are required to obtain a reliable kel.	Lambda_z from WNL. k_{el} will be presented as "Kel" in the TFL, and listed only If Adj $R^2 \le 0.80$ then parameter is flagged.
t _{1/2}		X	Terminal phase half-life expressed in time units. adjusted $\rm r^2$ greater than 0.80 is required to obtain a reliable $\rm t_{1/2}$.	HL_Lambda_z from WNL. $t_{1/2}$ will be presented as "t1/2" in the TFL. If Adj $R^2 \le 0.80$ then parameter is flagged.

EDSREP 009 T 01 G Page 22 of 53

Statistical Analysis Plan AZP20005-20005X Protocol: AZP-3601-CLI-001 Version Date: 26-Aug-2022

				VOIDION Bato. 20 7 tag 2022
Parameter	AND C Day 1	AND PART C DAY 28 and DAY 84	Description	SAS Programming Notes
CL/F			Apparent oral clearance, calculated as dose/AUC _{0-inf} .	CL_F_obs from WNL. If %AUC _{extra} >20% or Adj R ² ≤ 0.80 then parameter is flagged.
CL _{ss} /F		X	Apparent oral clearance at steady state, calculated as dose/AUC _{0-tau} where tau =6h (Parts B and C).	CLss_F from WNL CLss/F will be presented as "CLss/F" in the TFL.
Vz/F		Х	Apparent volume of distribution at terminal phase, calculated as (CL/F)/kel (Part A), or as (CLss/F)/kel (Parts B and C).	VZ_F_obs from WNL. If %AUC _{extra} >20% or Adj R ² ≤ 0.80 then parameter is flagged.
Rac		Х	Accumulation ratio, based on AUC _{0-tau} of Day 14 (Part B) or Day 28 (Part C) vs Day 1 where tau = 6h (Parts B and C).	Calculated in SAS. Rac will be presented as "Rac" in the TFL.
Adj R²	X		Goodness of fit statistic for the log-linear terminal elimination phase of the concentration-time profile identified by least-squares linear regression and adjusted for the number of points (minimum of 3) used in the estimation of k_{el} .	"Rsq_adjusted" from WNL. Adj R ² will be presented as "Adj R2" in the TFL and listed only.

Note: AUCs will be calculated using linear up / log down, expressed in units of concentration x time.

EDSREP 009 T 01 G Page 23 of 53

Version Date: 26-Aug-2022

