15.2.2 Pharmacokinetic Parameters

PK parameters for AZP-3601 will be estimated using non-compartmental methods with WNL under PK population set with data handling of PK Data Set and PK Data Set Info (if meaningful by the data obtained). Parameters will first be derived with values under LLOQ set as "BQL" (i.e. using PK Data Set). The inclusion of the informative PK concentrations ("No peak" and actual value between 0 and the LLOQ) in the calculation of the parameters will be performed for information only (i.e. using PK Data Set Info). Descriptive statistics will be conducted on both data sets if meaningful by the data obtained.

The plasma PK parameters will be estimated from the concentration-time profiles. In estimating the PK parameters, BQL values at the beginning of the profile will be set to zero. BQL values that occur after the first quantifiable point will be considered missing. Values that are embedded between BQLs, or quantifiable values occurring after two or more BQLs, will be set to missing at the discretion of the pharmacokineticist. Actual sampling times, rather than scheduled sampling times, will be used in all computations involving sampling times. If the actual time or dose time is missing, the scheduled time may be substituted in order to calculate the PK parameter.

EDSREP 009 T 01 G Page 24 of 53

Version Date: 26-Aug-2022

The points to be included in the k_{el} range will be determined by the pharmacokineticist after inspection of the semi-log concentration-time profiles. At least 3 points will be required to be used. The C_{max} data point will not be included.

Parameters based on %AUC $_{extra}$ >20% or Adj R 2 \leq 0.80 will be flagged but not excluded from statistical analysis.

Descriptive statistics (n, arithmetic mean, SD, geometric mean, geometric CV(%), median, min, and max) will be used to summarize the calculated PK parameters by study part and treatment (for Parts A and B) /cohort (for Part C). For t_{max}, only n, median, min and max will be presented.

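### Rac in Part C compares Day 28 with Day 1 AUC without a dose term, so a dose increase from Day 14 can be reported as accumulation

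*SAP*

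**What the plan says.** - **Definition.** The Rac row of SAP Table 1 (15.1.1.2) names AUC0-tau "of Day 14 (Part B) or Day 28 (Part C) vs Day 1 where tau = 6h (Parts B and C" and no dose. The programming note says only that the ratio is calculated in SAS. CLss/F, in the same table, is defined with dose in the numerator.
- **Dosing between the two days.** For patients who are not independent of active vitamin D, with oral calcium at or below 500 mg/day, on Day 14, the Protocol synopsis says that "the AZP-3601 dose will be increased and patients will be treated at this dose for the remaining duration of the treatment period", which ends on Day 28. For the rest, SAP 6.0 says: "Patients achieving independence from active vitamin D and reduction of oral calcium on Day 14 will remain at the same dose level".
- **Summary level.** SAP 15.2.2 uses descriptive statistics to "summarize the calculated PK parameters by study part and treatment (for Parts A and B) /cohort (for Part C". The general rule in SAP 8.1.4 is that "summary statistics will be calculated by treatment (and time point, if applicable", and SAP 8.5 says that treatment "refers to placebo and various dose levels of study drug in the TFL". In SAP 8.2.2, however, the Part C dose-level label is one per cohort and holds both doses. Cohort 1 is 20 µg "qd from Day 1 to Day 28 (may be increased to 40" µg.
- **Day 84.** The Protocol synopsis (PK Variables) lists, for Day 28 and for "Day 84 of Part C (Extension phase): Cmax, Ctrough, Cmin, tmax, kel, t1/2, AUC0-12, AUC0-24, CLss/F, Vz/F, and Rac". The Table 1 column in which Rac is marked covers Day 28 and Day 84, but the Rac description names only Day 28 for Part C.

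**The concern.** An accumulation ratio should show how much exposure builds up on repeated dosing of the same amount. Here the numerator and the denominator can come from different doses, and only in patients selected by their Day 14 response. The ratio then mixes true accumulation with the effect of the dose step. Because the cohort label holds both doses, the by-treatment and dose-level wording in 8.1.4 and 8.5 does not separate the two kinds of patient.

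PK after single and multiple doses in patients is a secondary objective, and Rac is one of the parameters named for it. A reader of the report could take a raised cohort Rac for build-up of the drug. The two cohorts could also show different values only because different shares were escalated.

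**Working it through.** The documents give no numerical Rac, so there is no figure to reproduce. The check is what the stated ratio returns when nothing accumulates.

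**Inputs from the documents**
- C1: 20 µg, rising to 40 µg (both documents). Dose ratio 40/20 = 2.0.
- C2 in the Protocol synopsis: 10 µg, rising to 20 µg. Dose ratio 20/10 = 2.0.
- C2 in SAP 8.2.2: 40 µg, rising to 60 µg. Dose ratio 60/40 = 1.5. SAP 6.0 words these as upper limits, so the SAP does not fix the ratio.
- About 12 patients per cohort.

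**Assumptions, not in the documents**
- True accumulation R = 1.
- AUC proportional to dose^b, with b = 1 as the base case and a range of 0.8 to 1.2.
- The number escalated, k, is 3, 6 or 9 of 12, for illustration only.

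**One patient.** Rac as written = R × (dose on Day 28 / dose on Day 1)^b.
- Not escalated: 1.0.
- Escalated, b = 1: 2.0 at dose ratio 2; 1.5 at dose ratio 1.5.
- Escalated, b = 0.8 to 1.2: 1.74 to 2.30 at ratio 2; 1.38 to 1.63 at ratio 1.5. The artefact does not need exact proportionality.

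**One cohort, b = 1.** With dose ratio f, the geometric mean is f^(k/12) and the arithmetic mean is (12 − k + k·f)/12. The geometric CV is √(exp(s²) − 1), where s² = [k(12 − k)/(12 × 11)] × (ln f)².

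| k of 12 escalated | Geometric mean, f = 2 | Arithmetic mean, f = 2 | Geometric CV, f = 2 | Geometric mean, f = 1.5 |
|---|---|---|---|---|
| 0 | 1.00 | 1.00 | 0% | 1.00 |
| 3 | 2^0.25 = 1.19 | 1.25 | 32% | 1.11 |
| 6 | 2^0.5 = 1.41 | 1.50 | 37% | 1.22 |
| 9 | 2^0.75 = 1.68 | 1.75 | 32% | 1.36 |
| 12 | 2.00 | 2.00 | 0% | 1.50 |

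Every departure from 1.00, and all of the CV, comes from the dose mix.

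**After dose normalisation.** (AUC Day 28 / dose Day 28) / (AUC Day 1 / dose Day 1) = R × f^(b − 1). With R = 1 and b = 1 this is 1.00 for every patient, whatever k is. With b = 0.8 to 1.2 it is 0.87 to 1.15 at ratio 2 and 0.92 to 1.08 at ratio 1.5.

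**How large could true accumulation be?** SAP 7.1 expects quick elimination but gives no half-life. For assumed half-lives of 15 to 90 minutes, superposition of doses 24 hours apart gives a true Rac of at most 1.00002. In that range the dose step would be almost the whole of the reported value.

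**The case against.** The strongest reply is that the row is a description and not a formula. Saying that Rac is based on two AUCs leaves room for a programmer to normalise by dose. The text of 15.2.2.1 (Dose-Proportionality) and the table shells cannot be seen, and only the synopsis and schedules of the Protocol are visible. The synopsis does plan an analysis of variance for dose-proportionality, so dose is considered somewhere. This stands as a limit on certainty: a reader should not infer that the report will certainly show 2.0 for escalated patients. It does not remove the point. The Rac row refers to no normalisation, and two programmers following it could return 2.0 and 1.0 for the same patient.

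A second reply is that the cause can be traced. Exposure is listed by subject, SAP 14.0 tabulates dose increases, and Day 28 CLss/F carries dose. This also stands in part, and it limits the harm. But the SAP 14.0 items for the main period are Yes/No flags against Day 1, summarised as exposure and not linked to Rac. The reported ratio would still be wrong for escalated patients.

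A third reply is that the escalated shares are invented and that no comparison of Rac between cohorts is planned. Both are true. The cohort figures show sensitivity and are not forecasts. If nobody is escalated, the problem does not arise.

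**Conclusion.** On the visible text, Part C Rac is wrong as defined for any patient whose dose changes between Day 1 and Day 28. Under approximate proportionality and no true accumulation it reads about 2.0, or 1.5 for C2 if the SAP doses apply. The cohort value moves with a share escalated that the documents do not give. The Protocol and SAP passages on C2 doses must be reconciled before the size for that cohort can be stated. The change should be made, but the consequence is modest.

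Three stronger readings are tempting and are not supported:
- *That this threatens the trial's main conclusions or the dose decision between cohorts.* The primary objective is safety and tolerability, SAP 8.4.3 plans no formal test, and Rac is not among the interim outputs listed in SAP 7.2.
- *That Day 84 Rac will be distorted still more by titration.* The Protocol lists Rac on Day 84, but the SAP's Rac description names only Day 28 for Part C. Whether it will be derived on Day 84 is an ambiguity to settle, not a demonstrated error.
- *That ending PK sampling at 2 hours while using a 6-hour window biases Rac.* With the same window and the same elimination on both days, the window cancels in the ratio.

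**What to change.** 1. In SAP Table 1, define Part C Rac as (AUC0-tau on Day 28 / actual dose on Day 28) divided by (AUC0-tau on Day 1 / actual dose on Day 1).
2. Also present Rac for patients whose Day 28 dose equals their Day 1 dose.
3. State whether Rac is derived on Day 84. If it is, use the same dose-normalised form.
4. If 15.2.2.1 or the shells already contain such a rule, refer to it in the Rac row.

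Two additions are optional: a Day 14 to Day 1 ratio for patients still on the Day 1 dose at the Day 14 profile, and a display of Cmax and AUC by actual dose on the profile day.

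The cost is SAP wording and programming. No extra samples are needed, and actual doses are already in the exposure data, although the dose ratio itself must be derived. There are two downsides. Normalisation assumes approximate proportionality, with the error range shown above. The unchanged-dose subset does not need that assumption, but it is small and is selected on Day 14 response, so it may not represent the cohort. Showing both lets each check the other.

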15.2 Pharmacokinetic Summaries

15.2.1 Pharmacokinetic Concentrations

All AZP-3601 plasma concentrations will be reported under PK population set with data handling of PK Data Set and PK Data Set Info (for information only). Under PK Data Set, analyses on the concentrations will be performed with values under LLOQ set as "BQL". Under PK Data Set Info, AZP-3601 plasma concentration will include the concentrations extrapolated from the analyte response under the LLOQ (for information purpose); values under LLOQ will either be a "No peak" or an actual value between 0 and the LLOQ value (i.e. 50 pg/mL). The Inclusion of the informative PK concentrations ("No peak" and actual value between 0 and the LLOQ) in the analyses under PK Data Set Info will be performed for information only. The conventions to be applied for "No peak" under PK Data Set Info will be the same as the one use for BQL under PK Data Set. Descriptive statistics and PK concentration plots will be conducted on both data sets.

Descriptive statistics (n, 0<n<LLOQ, n with imputed 0, arithmetic mean, SD, geometric mean, geometric CV(%), median, min, and max) will be used to summarize the plasma concentrations for AZP-3601 by scheduled time point by study part and treatment (for Parts A and B)/cohort (for Part C). Plasma concentrations for AZP-3601 below the quantifiable limit (BQL) will be set to zero in the computation of descriptive statistics. Geometric means and geometric CV(%) will be presented as 'NC' (not calculable) if there is at least one BQL value imputed by zero.

Linear and semi-logarithmic plots of the arithmetic mean plasma concentration with SD by scheduled
sampling time will be provided by study part and
plots will show time in hours. In Part
C, the MAD treatments will be presented in one plot per day. In addition, overlay plots for the MAD
treatments will be presented,
showing Day 1, Day 14 and Day 28 in one plot for Part C (one plot per cohort). If more than half of the subjects for a given timepoint have BQL values, then no mean profiles will be provided.
Combined individual concentration-time profiles will be presented graphically on both a linear and a semi-logarithmic scale for each

Linear and semi-logarithmic plots of the individual plasma concentrations by actual sampling times will be provided by subject. These plots will show time in hours. MAD plots will show the complete profile. Individual plots will use the BQL handling procedure described below for "Pharmacokinetic Parameters".

All individual subject plasma concentration data will be listed, including time deviations and comments.

